10.6.2.3 Electrocardiogram (ECG)

All on-study ECG data will be reviewed for each subject.

10.6.2.4 Physical Examination

Physical examination results will be reviewed for each subject. Depending on the size and scope of change in weight and BMI, summaries may be provided.

10.6.2.5 Laboratory Test Results

Hematology, chemistry and urinalysis data will be reviewed for each subject. Depending on the size and scope of changes in laboratory data, summaries of laboratory data over time and/or changes from baseline over time may be provided. Liver function abnormalities will be summarized.

10.6.2.6 Neurologic Assessment

Neurological assessment data will be reviewed for each subject.

10.6.3 Pharmacokinetic Endpoints

Serum AMG 334 concentrations will be determined using a validated assay. Individual serum concentration-time plots for AMG 334 will be presented for each subject as well as mean concentration-time plots for each treatment group. PK parameters C_{1 hour}, and AUC_{84d} will be estimated using either compartmental (eg, PK modeling) or non-compartmental methods. Actual dosing and sampling times will be used for

Statistical Analysis Plan: 20140207

Date: 17 May 2017 Page 25

calculation of PK parameters. Summary statistics will be generated for each PK parameter for each treatment group and provided by CPMS. The PK analysis set will be used for these analyses.

10.6.4 AMG 334 Antibody Assessment

Binding antibody and neutralizing antibody formation will be assessed at predose and at various time points throughout the study including EOS. Antibody data will be listed for each subject. The incidence and percentage of subjects who develop anti-AMG 334 antibodies (binding and if positive, neutralizing) at any time will be tabulated by treatment group.

10.7 Exploratory Endpoint(s)

10.7.1 Migraine-like Attacks (MLA) and Headaches

The reduction in severity of MLA and headaches by AMG 334 within 24 hours after infusion of PACAP-38 on day 8 will be assessed and summarised based on a severity score (0-10; 0=pain free; 10=extreme pain). Severity of MLA and headaches will be analysed separately using a repeated measure analysis of variance model. Independent variables will be treatment, hour, and treatment by hour interaction. Subject will serve as a random effect. For each treatment by hour combination, least square means, ratio to placebo, 95% confidence intervals and corresponding nominal p-values for the null hypothesis of no difference from placebo will be presented. Graphical summaries of severity scores will also be provided. For SAS code, see Appendix A1.

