3. EXPERIMENTAL PLAN

3.1 Study Design

This is a randomized, double-blind, placebo-controlled, parallel-group study in subjects with episodic migraines. This study will evaluate the efficacy of AMG 334 as measured by inhibition of PACAP-38 induced migraine-like attacks after a single dose of AMG 334. Migraine-like attacks (MLA) will be defined as attacks fulfilling one of the two criteria:

(1) Headache fulfilling criteria C and D for migraine without aura (IHS 2004)

- C. Headache has at least two of the following characteristics:
 - unilateral location
 - pulsating quality
 - moderate or severe pain intensity (≥ 4 on headache questionnaire)
 - aggravation by or causing avoidance of routine physical activity

D. During headache at least one of the following:

- nausea and/or vomiting
- photophobia and phonophobia

(2) Headache described as mimicking usual migraine attack treated with triptan.

Part A: PACAP-38 Dose Selection Phase: There are a number of published clinical studies in which pituitary adenylate cyclase-activating polypeptide-38 (PACAP-38) was used to trigger MLA in migraneurs (Schytz et al, Brain 2009; Amin et al, Cephalagia 2011; Amin, Brain 2014). In those studies, 10 pmol/kg/min over 20 minutes (total dose 200 pmol/kg) was administered. Approximately 90% of migraineurs experienced a headache and approximately 66% of the same migraineurs experienced MLA with a median time of headache onset of 4 hours, though the half-life of PACAP-38 is only 3.5 minutes. As PACAP-38 is involved in various biological processes, including sensory processing, vasodilation, inflammation, and nociceptive transmission (Dickinson et al., 1999; Vaudry et al., 2000), nearly all healthy subjects and migraineurs also experienced the expected adverse events of flushing and heat sensation, along with a transient elevation in heart rate and blood pressure (Birk et al, Regulatory Peptides 2007; Schytz et al, Brain 2009; Amin et al, Cephalagia 2011; Amin, Brain 2014) (see Investigator Brochure for details).

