10.5.4 Exploratory Endpoints

10.5.4.1 Migraine-like Attacks (MLA) and Headaches

The reduction in severity by AMG 334 of MLA and headaches within 24 hours after infusion of PACAP-38 will be assessed and summarised based on a severity score (0-10; 0=pain free; 10=extreme pain). For MLA and headaches separately severity scores will be analysed using a repeated measure analysis of variance model.

Independent variables will be treatment, hour and treatment by hour interaction. Subject will serve as a random effect. For each treatment by hour combination, least square means, ratio to Placebo, 95% confidence intervals and p values for the null hypothesis of no difference from placebo will be presented. Graphical summaries of severity scores will also be provided. In addition, descriptive statistics will be provided for the duration of MLA and headaches.

Descriptive summaries of measured characteristics of MLA and headaches, such as localization and accompanying symptoms and pre-monitory symptoms, within 24 hours after infusion with PACAP-38 will be presented for each treatment group.

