10.1 General Principles

Unless otherwise stated, data from PACAP-38 responders who go on to be randomized and receive IP will be summarized. Data from PACAP-38 non-responders, and data from

Statistical Analysis Plan: 20140207

Date: 17 May 2017 Page 22

PACAP-38 responders that do not receive IP, will not be included in the summaries, but will be reviewed.

Unless otherwise specified, data will be summarized using the safety analysis set, by actual treatment group (AMG 334 or Placebo).

Descriptive statistics will be provided for selected demographics, safety and PK data. Descriptive statistics on continuous measurements will include means, medians, standard deviations (and standard errors for post-baseline data), quartiles, and ranges, while categorical data will be summarized using frequency counts and percentages. Where statistical models are applied to the data, estimates of the differences/ratios, confidence intervals and corresponding p-values will be presented, as applicable. However, these are for descriptive and illustrative purposes only and to aid interpretation of the data; no formal statistical hypothesis testing will be performed.

When data are summarized by time, the values recorded against the scheduled time points, including any time windows specified in the protocol will be used.

When assessing minimum/maximum increases or decreases over the study, all assessments, including unscheduled assessments will be used.

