10.7.2 Duration of Migraine-like Attacks (MLA) and Headaches

Descriptive statistics will be provided for the duration of MLA and headaches by treatment group.

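### SAP 10.7.1 does not say which subjects or scores enter the separate MLA and headache severity models; on the natural reading the MLA model compares groups selected on the primary outcome

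*SAP*

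**What the plan says.** One of the exploratory objectives (SAP 2.3) is to evaluate whether AMG 334 reduces the severity of induced MLAs and headaches. SAP 10.7.1 measures this "based on a severity score (0-10; 0=pain free; 10=extreme pain", and then says: "Severity of MLA and headaches will be analysed separately using a repeated measure analysis of variance model". Protocol 10.5.4.1 agrees: "For MLA and headaches separately severity scores will be analysed using a repeated measure analysis of variance model". On the model terms the SAP says: "Independent variables will be treatment, hour, and treatment by hour interaction". Subject is a random effect, and each treatment-by-hour combination is to be reported with "least square means, ratio to placebo, 95% confidence intervals and corresponding nominal p-values".

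No sentence in SAP 10.7.1 names the population of either model. The general rule in SAP 10.1 is: "Unless otherwise specified, data will be summarized using the safety analysis set, by actual treatment group (AMG 334 or Placebo". SAP 7.1 defines that set as everyone who receives IP, and SAP 11 takes subjects who never receive PACAP-38 out of the summaries.

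Pain also enters the definition of an MLA. One of the four criterion C features, of which two are needed, is "moderate or severe pain intensity (≥ 4 on headache questionnaire" (protocol 3.1; repeated in SAP 3.1). The part of the headache questionnaire that can be read (protocol Appendix D) shows one pain scale.

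**The concern.** If every challenged subject entered both models with the same score, the two models would be identical and the word separately would have no meaning. Something must therefore distinguish them. Either subjects are split by type of event, or scores that do not belong to an MLA are set to 0. The text gives no rule, and the plain sense of severity of MLA is the scores of subjects who had one.

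On that reading the comparison is made among subjects chosen by an event that the drug is meant to prevent. The protection given by randomisation is lost, and prevented attacks do not count. Because the pain score helps to decide MLA status, lowering a subject's pain can move that subject out of the MLA model instead of registering there as a benefit. If AMG 334 removes mainly the milder attacks, those that remain will look worse than placebo attacks.

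If the choice stays open until treatment codes are known, it can change the size and even the sign of the effect reported against a named objective.

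**Working it through.** **Inputs from the documents.** MLA rates of 70% on placebo and 20% on AMG 334 (SAP 3.2, used as MLA rates in the SAP 8.2 tables); 8 per arm at the interim and 18 per arm in full, with the decision rules (SAP 8.2). The documents give no power or sample size for the severity models.

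**Check of the planning figure.** I enumerated the two-stage rule exactly: fail if placebo MLAs are 3 or fewer of 8, or if AMG 334 has more than placebo; early success if the difference is at least 6/8; otherwise add 10 per arm and apply the one-sided Fisher test at 0.1. At 70% v 20% the success probability is 90.95%, against the stated 91%. The rates and rules are therefore a sound basis.

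**Size of an MLA-only model.** Expected number = n × rate.

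| n per arm | Placebo | AMG 334 | P(no AMG 334 subject) | P(at most 1) |
|---|---|---|---|---|
| 18 | 18 × 0.7 = 12.6 | 18 × 0.2 = 3.6 | 0.8^18 = 1.8% | 9.9% |
| 8 | 8 × 0.7 = 5.6 | 8 × 0.2 = 1.6 | 0.8^8 = 16.8% | 50.3% |

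At 18 per arm, P(3 or fewer on AMG 334) = 50.1%.

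The row for 8 per arm does not condition on the trial having stopped. At these rates P(early success) = 19.5% and P(any interim stop) = 6.0% + 19.5% = 25.5%. No AMG 334 subject with an MLA together with early success needs at least 6 placebo MLAs: 0.168 × 0.552 = 0.0926. Given an efficacy stop, the chance that the AMG 334 arm is empty is 0.0926/0.195 = 47%. Given any interim stop it is 0.1023/0.2549 = 40%.

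**What each reading would show.** This is an illustration whose severity values are assumptions and not figures from the documents: one peak score per subject, attack severity normal with placebo mean 6 and SD 2, clipped to 1-10, 0 without an attack, 18 per arm, 4,000 trials, and a t-test at two-sided 0.05 in place of the repeated-measures model. Differences are AMG 334 minus placebo; rejection rates are in brackets.

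| Assumed truth | MLA-only | All subjects, 0 when pain free |
|---|---|---|
| 70% v 20%, remaining attacks equally severe | about 0 (5%) | -3.0 (84%) |
| 70% v 20%, remaining attacks 1 point worse | +0.95 (13%) | -2.8 (74%) |
| 70% v 20%, remaining attacks 2 points milder | -2.0 (36%) | -3.4 (95%) |
| 70% v 70%, attacks 2 points milder | -1.9 (66%) | -1.35 (29%) |

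In the first three rows about 10% of trials had fewer than two MLA subjects in an arm; they are left out of the MLA-only column.

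**The link between score and status.** A second illustration assumes peak pain normal with mean 5 and SD 2.2, clipped to 0-10, and simplifies MLA to a score of 4 or more. A true 2-point shift gives a difference of 1.9 in all subjects but 0.7 among MLA subjects; a 3-point shift gives 2.8 and 1.0. The simplification rules out mild MLAs, which the plan allows, so this shows a mechanism and not an expected size.

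**The case against.** A reader might infer that the SAP confines the MLA model to subjects whose attack was not prevented. It does not say so. The default population is the safety analysis set, the scale has a value for no pain, and separate models could use all subjects with the MLA score set to 0 when there was none. SAP 10.7.1 also points to code in Appendix A that does not appear in the available text and might define the data sets. The questionnaire is only partly readable, so the existence of a single score rests on SAP 10.7.1 and on the one visible scale. This part of the objection stands: restriction to MLA subjects is the natural reading, not a stated rule.

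A reader might also infer that an MLA-only model cannot show reduced severity. That is too strong. In the third and fourth rows above it finds the milder attacks, though with selection and, where prevention is large, few subjects.

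Nor does a pain score below 4 by itself end MLA status. Two other criterion C features suffice, the second MLA definition has no pain threshold, and Part A expressly admits mild MLAs. A subject who does leave the MLA group can still contribute to the headache model.

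The all-subject model has its own limit. With prevention and unchanged attack severity it shows -3.0, so it reports prevention as lower pain. In the fourth row it is the less sensitive of the two.

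Finally, SAP 10.1 treats model results as descriptive, SAP 10.7.1 calls the p-values nominal, and no decision rule uses them. What these arguments leave untouched is that the text does not define the two data sets, and that one available reading abandons the randomised comparison.

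**Conclusion.** The concern holds as a gap in specification with a foreseeable bad outcome. One described score is to be analysed in two models whose subjects and scoring are not stated. If the MLA model is limited to subjects with an MLA, it conditions on the primary outcome and would hold about 12.6 v 3.6 of 18 per arm, or 5.6 v 1.6 of 8, at the plan's own rates. It could then understate or reverse a real reduction in severity. The counts rest only on those rates; the size and direction of the distortion rest on assumed severities. The consequence is confined to an exploratory objective, and the primary Fisher comparison is unaffected. The summary of duration needs no change: SAP 10.7.2 already limits it to description ("Descriptive statistics will be provided for the duration of MLA and headaches by treatment group").

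**What to change.** In SAP 10.7.1, make the analysis of reduced severity a single repeated-measures model of the 0-10 score. Include all randomised subjects who received IP and the Day 8 PACAP-38 challenge, and score time points without headache as 0 whatever the subject's MLA status. Label the result as combining prevention with milder attacks. Keep severity among subjects with an MLA as a descriptive summary by arm, without between-arm p-values or confidence intervals. If the Appendix A code already defines the data sets, bring it into line with this text.

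The cost is a few lines of SAP wording. One model replaces two and no new data are needed. What is given up is the set of nominal MLA-only p-values and, if attacks become milder without being prevented, some sensitivity.

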2.3 Exploratory

- To evaluate the reduction in severity of PACAP-38 induced migraine-like attacks and headaches by AMG 334
- To evaluate the duration of PACAP-38 induced migraine-like attacks and headaches by AMG 334
- To evaluate the safety and tolerability of a single intravenous (IV) dose of exogenous PACAP-38
- To evaluate CGRP and PACAP-38 levels in migraine patients

3. Study Overview

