If the PI, MM, and GSO or designee decides not to proceed with enrollment into a subsequent cohort, then a Safety Review Meeting or DLRM will be held after the last dosed cohort. The Safety Review Meeting or DLRM voting members will decide whether or not to proceed with enrollment in Part B Randomization (AMG 334 or Placebo) Phase and if the decision is made to proceed, the Safety Review Meeting or DLRM voting members will select the appropriate PACAP-38 dose from the Dose Selection Phase, Part A. The decision to proceed with Part B of the study will be based on the goal of ensuring subject safety and ideally triggering headache in all subjects within a given cohort and moderate to severe MLAs in the majority of subjects within the same cohort. However, the trigger of headaches in the majority of subjects within the same cohort and mild, moderate or severe MLAs in the majority of subjects within the same cohort may be considered acceptable to advance to Part B of the study.

Part B: Randomization (AMG 334 or Placebo) Phase: PACAP-38 responders from part A, as well as PACAP-38 naïve subjects (those who never received PACAP-38

Statistical Analysis Plan: 20140207

Dated: 17 May 2017 Page 9

before) can enter screening in part B. Subjects will be enrolled in Part B following the 21 day screening period. There will be a minimum duration of 2 weeks between the first and second PACAP-38 doses for all subjects enrolling in Part B of the study.

Eligible PACAP-38 responders from Part A will immediately be randomized to receive either AMG 334 or placebo, whereas eligible PACAP-38 naïve subjects will first enter a PACAP-38 challenge phase. Only PACAP-38 responders (those who experienced a MLA within 24 hours after the challenge) will be randomized to receive either AMG 334 or placebo.

A minimum of 16 and a maximum of 36 PACAP-38 responders will be randomized to receive AMG 334 or Placebo.

PACAP-38 Responders from Part A

On Day 1, PACAP-38 responders from Part A will receive 140 mg IV AMG 334 over 30 minutes or placebo, in a one to one allocation ratio. On Day 8, the subjects will be administered the dose of PACAP-38 determined from the PACAP-38 Dose Selection Phase (Part A).

PACAP-38 Naïve Subjects

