4.2 Planned Covariates and Subgroups

Planned covariates consist of baseline measures. No subgroup analysis is planned.

5. Hypotheses and/or Estimations

A single dose of 140 mg IV of AMG 334 will inhibit MLAs in subjects challenged with PACAP-38.

6. Definitions

Adverse Event (AE)

Serious Adverse Event (SAE):

SAE determined by the flag indicating if the adverse events is serious on the AE eCRF page will include these that occur after signing the informed consent and up to and including end of study (EOS).

Treatment-Emergent AE:

A treatment-emergent AE is that occurs on or after the initial dose of investigational product (IP) as determined by the flag indicating if the AE started prior to the first dose on the AE eCRF and up to and including end of study.

Disease-Related AE:

Migraine will be considered a disease related event; however, worsening of migraines (ie. increased frequency and/or intensity) should be reported as an AE.

Baseline

Unless otherwise stated, baseline will be defined as the last assessment taken prior to the first IP (AMG 334 or placebo) administration (ie, Day 1 pre-dose or Screening if Day 1 pre-dose is not available).

Statistical Analysis Plan: 20140207

Date: 17 May 2017 Page 15

Change from Baseline:

The arithmetic difference between a post-baseline value and the baseline value:

Change (absolute) from Baseline = (Post-baseline Value – Baseline Value)

Change (percent) from Baseline = [(Post-baseline Value – Baseline Value) / Baseline Value] x 100

Body Mass Index (BMI)

BMI will be calculated as {weight (kg)/ [height (m)]²} in the clinical database.

Columbia Suicide Severity Rating Scale (C-SSRS)

The C-SSRS is a clinical rating of suicidal ideation and behavior. Refer to Appendix E and Appendix F in the protocol for complete details on the C-SSRS. The Baseline/Screening version of the C-SSRS will be administered at screening (Day -21 to -2), while the Since Last Visit version of the C-SSRS will be administered at the other time point(s) on the Schedule of Assessments. Reports of suicidal ideation with intent to act (endorse item 4 or 5) and reports of actual, aborted, or interrupted suicide attempts or a behavior preparatory for making an attempt indicate subjects at high risk for suicide. If such reports are identified, the investigator is to appropriately manage the subject in accordance with standard of care.

End-of-Study (EOS)

The EOS is the last planned clinical visit for each subject enrolled in this study.

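### The exploratory severity model in SAP 10.7.1 omits each subject's severity at the PACAP-38 challenge given before AMG 334 or placebo; adding it could improve precision cheaply

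*SAP*

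**What the plan says.** SAP 3.1 places a PACAP-38 challenge before investigational product (IP) for everyone randomised. For PACAP-38-naive subjects: "Only PACAP-38 responders (those who experienced a MLA within 24 hours after the challenge) will be randomized to receive either AMG 334 or placebo". Subjects who responded in Part A skip that step because they have already been challenged: "Eligible PACAP-38 responders from Part A will immediately be randomized to receive either AMG 334 or placebo". Naive subjects receive the same selected dose at both challenges, and at least two weeks separate the first and second doses.

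One exploratory objective in SAP 2.3 is "To evaluate the reduction in severity of PACAP-38 induced migraine-like attacks and headaches by AMG 334". SAP 10.7.1 addresses it with the 0-10 pain score "within 24 hours after infusion of PACAP-38 on day 8 will be assessed and summarised". The model is a repeated-measures analysis of variance: "Independent variables will be treatment, hour, and treatment by hour interaction", with subject as a random effect. No score from the challenge before IP is among the terms.

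SAP 4.2 states: "Planned covariates consist of baseline measures". It names none. The general baseline definition in SAP section 6 is the last assessment before first IP, explained as Day 1 pre-dose or Screening.

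**The concern.** The first challenge shows how severe each subject's induced attack is without AMG 334. That is a natural baseline for an objective about reduced severity, and the plan appears to collect it anyway. With 8 to 18 subjects per arm, chance differences between arms in untreated severity can be appreciable, and an unadjusted model leaves them in the treatment estimate.

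The SAP also does not fit together here. The primary and headache comparisons use Fisher's exact test, and the other efficacy and safety analyses are descriptive. The 10.7.1 model is therefore the only comparative model that could carry a covariate, and it carries none, so the statement in 4.2 has no effect. The general baseline definition does not fill the gap. In the supplied protocol (Appendix D) the Day -1 questionnaire page asks about usual migraine frequency and rescue medication, not the severity of an induced attack.

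At stake is the width of the confidence intervals for an exploratory endpoint.

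**Working it through.** **Is a first-challenge score likely to exist?** In the supplied protocol, Table 3 (Part A) and Table 2 (Part B, Day 8) both schedule the headache questionnaire at 0, 0.25, 0.5, 1, 2, 3, 4, 8 and 24 hours. The questionnaire in Appendix D has a pain scale whose upper anchor is 10. For the naive subjects' challenge period the SAP refers to Table 2 of Protocol Amendment 4, which is not among the documents. Timed scoring there is inferred from the common questionnaire.

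**Does the random subject effect do the same job?** No. It models the correlation among one subject's Day 8 hours. It removes no between-subject variance from the comparison of arms.

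**The plan's own figure.** The SAP gives no power or precision figure for severity. Its only such figure is the 91% chance of success on the primary endpoint (70% against 20% MLA). Exact enumeration of the four decision rules gives 0.910, so it reproduces. It does not involve the severity model.

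**Effect of adjustment.** Inputs: N = 16 or 36, allocated 1:1 (SAP 3.1). The correlation r between first-challenge and Day 8 severity is not in the documents; 0.3 to 0.7 is assumed. With the cost of estimating the covariate included,

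variance ratio (adjusted / unadjusted) = (1 − r²) × (1 + 1/(N − 4)).

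The second factor is 1 + 1/32 = 1.031 at N = 36 and 1 + 1/12 = 1.083 at N = 16.

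| r | 1 − r² | Ratio, N = 36 | SE ratio | Ratio, N = 16 | SE ratio |
|---|---|---|---|---|---|
| 0 | 1.00 | 1.031 | 1.016 | 1.083 | 1.041 |
| 0.3 | 0.91 | 0.938 | 0.969 | 0.986 | 0.993 |
| 0.5 | 0.75 | 0.773 | 0.879 | 0.812 | 0.901 |
| 0.7 | 0.51 | 0.526 | 0.725 | 0.552 | 0.743 |

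At N = 36 the adjusted analysis is worth 36/0.938 ≈ 38, 36/0.773 ≈ 47 and 36/0.526 ≈ 68 unadjusted subjects.

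**Break-even.** Setting the ratio to 1 gives r² = 1/(N − 3). So r = 1/√33 ≈ 0.17 at N = 36 and 1/√13 ≈ 0.28 at N = 16, or about 0.2 and 0.3. Below these values adjustment costs variance, at most 3.1% and 8.3% (the r = 0 row).

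**Responder selection.** Only responders are randomised, which may narrow the spread of first-challenge severity. As an illustration, suppose the lowest 34% were excluded (the complement of the historical 66%). In simulation at 18 per arm, r of 0.3, 0.5 and 0.7 before selection becomes about 0.21, 0.36 and 0.55 among responders. The variance ratios become 0.98, 0.89 and 0.73, which are gains of about 2%, 11% and 27%.

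**The case against.** The strongest reply is that this is optional efficiency. Severity is exploratory, its p-values are nominal, and SAP 10.1 says model results are descriptive with no formal testing. That stands, and it sets the weight of the point.

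The size is uncertain. A reader might infer from 1 − r² alone that the standard error falls by about 5%, 13% or 29%, and that intervals must narrow. The documents do not support this. They give no r, small-sample cost and responder selection both reduce the gain, and a low r would reverse it. Nor does a chance imbalance pass into the estimate in full: about r times a standardised imbalance does.

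The formula also does not match every planned output. SAP 10.7.1 reports a contrast at each hour, for which the relevant r is the correlation with that hour's score and may be lower. Nothing here applies to the ratio to placebo. Nor does SAP 10.7.1 say whether subjects without a Day 8 MLA enter the MLA severity model. If they do not, the planning rate leaves about 0.20 × 18 = 3.6 AMG 334 subjects in a subset formed after randomisation, where the formula does not hold.

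Part A responders may have been challenged at a dose other than the one selected for Part B, so their scores may not be like for like. Rescue medication is allowed (Protocol 6.9), so a 24-hour mean partly reflects treatment of the first attack.

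It may also be tempting to say that the first-challenge score is discarded after serving as a yes/no gate. The text does not say so. The gate is MLA occurrence, in which pain of at least 4 is one of four features of which two are needed, and the triptan criterion needs no score. SAP 10.1 says data from randomised responders who receive IP will be summarised unless otherwise stated. The supportable statement is only that the score is absent from the severity model.

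**Conclusion.** The omission holds on the text and is minor. SAP 10.7.1 lists no pre-treatment severity term, SAP 4.2 implies that there should be one, and the baseline definition does not identify it. For assumed r between 0.3 and 0.7 among randomised subjects, adjustment would cut the variance of the treatment contrast by about 6% to 47% at N = 36 and 1% to 45% at N = 16. If those correlations apply before responder selection, the illustrative gain at N = 36 is about 2% to 27%. The worst case is a loss of about 3% or 8%.

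These figures apply to an analysis including all randomised subjects. They are conditional on first-challenge scores having been recorded in the naive subjects, which cannot be confirmed without Amendment 4. The text of SAP Appendix A, where the code should be, is also not available, so a baseline term in the code cannot be ruled out.

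A reader might infer that the planned comparison is biased or that the trial's main conclusion is weakened. Neither follows: the unadjusted randomised comparison is unbiased, and the primary Fisher test, the interim rules and the 91% figure do not depend on this model.

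**What to change.** Before unblinding:

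- In SAP 10.7.1, add the subject's severity at the challenge before IP as a covariate in both severity models. Name one summary in advance, such as the peak 0-10 score over 24 hours or the score at the matching hour.
- Add a term for entry route (Part A or naive) or for first-challenge dose.
- State whether subjects without a Day 8 MLA are in the MLA severity model.
- Amend SAP 4.2 to name this covariate, and add the challenge score to the baseline definition for this analysis. If the sponsor prefers no adjustment, 4.2 still needs correcting.

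The cost is a few SAP sentences and one or two model degrees of freedom, with no new data if the scores exist. The entry-route or dose term has its own small-sample cost, which is not in the figures above and weighs most at 8 per arm.
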